#### ***Visit 4 (V4) – Treatment Dose / Day 0***

This intervention will occur 1 week following the safety dosing session (V3). On the day of the intervention the following procedures will take place:

- Study intervention administration (Section 5.0): 1 oral dose of 25 mg of psilocybin administered in conjunction with supportive therapy (PAT).
- Vital signs (blood pressure and pulse) will be taken every 1.5 hours during this session.
- At least one therapist will be present in the room at all times during PAT and be available to respond to participants' physical and emotional needs
- Participants will be instructed to lie on a bed in a non-clinical environment, and therapists will encourage participants to focus their attention inward and stay with any experience that arises. To enhance inward reflection, a pre-selected music playlist will be played. Administration of questionnaires or other instruments to be completed at the end of the dosing session when the acute effects of psilocybin have resolved:
  - Study team or therapist administered:
    - 11D-ASC to assess the acute drug effects.
    - UKU Side Effect Scale
- The participant will be discharged 6-8 hours post-dosing when, in the opinion of the study PI (or delegate), the acute effects of psilocybin are resolved. The participant must be accompanied home by a caregiver who will remain with them for up to 24 hours after the dose was administered.

- Rescue medications are permitted during this visit as outlined in Section 5.6.

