#### **4.4.2 Exclusion Criteria**

An individual who meets any of the following criteria will be excluded from participation in this clinical trial:

1. Pregnant as assessed by a urine pregnancy test at Screening (V1) or individual's that intend to become pregnant during the study or are breastfeeding;
2. Treatment with another investigational drug or other intervention within 30 days of Screening (V1);
3. The presence of an unstable seizure disorder as defined by having not been seizure-free for at least 6 months or anticonvulsant treatment has not been stable for at least 4 weeks;
4. The presence of any clinically significant or unstable medical conditions, including cardiovascular, liver, kidney, pulmonary disease, presence of known congenital brain malformation, as per investigator assessment based on medical history and chart review;
5. Moderate or severe DSM-5 diagnosis of an alcohol or substance use disorder in the past 12 months;
6. Any DSM-5 lifetime diagnosis of a schizophrenia-spectrum disorder, psychotic disorder (unless substance induced or due to a medical condition), bipolar I or II disorder, paranoid personality disorder, or neurocognitive disorder as determined by medical history and the SCID-5-CV clinical interview;
7. Any first-degree relative with a diagnosis of schizophrenia-spectrum disorder; psychotic disorder (unless substance-induced or due to a medical condition); or bipolar I or II disorder as determined by the family medical history form and discussions with the participant;
8. Presence of a relative or absolute contraindication to psilocybin, including a drug allergy, recent stroke history, uncontrolled hypertension, low or labile blood pressure, recent myocardial infarction, cardiac arrhythmic, severe coronary artery disease, or moderate to severe renal or hepatic impairment;

9. Substantial lifetime use (>10 years total) or recent use (past 6 months) of ketamine, psychedelics, or MDMA;
10. Any other clinically significant physical illness, including chronic infectious diseases or any other major concurrent illness that, in the opinion of the investigator, may interfere with the interpretation of the study results or constitute a health risk for the participant if they take part in the study;
11. Have active suicidal ideation with intent and plan as determined by SBQ-ASC.
12. Are currently undergoing psychotherapy or have undergone psychotherapy within 12 weeks prior to Screening.

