### **Washout Period: Minimum of 2-Weeks**

Participants who are on concomitant medications (Section 5.6) must be tapered off at least 2 weeks prior to Baseline (V2). The plan for tapering off medications will be determined at the first screening visit (V1) with the participant and the study physician. During the washout period, the study physician will have weekly appointments with the participant to check how they are doing and ensure they are safe. The weekly appointments can be scheduled in-person or remote (via telephone/WebEx) based on the participant's preference and at the discretion of the study physician. Participants will be assessed for suicidality with the SBQ-ASC at each contact/visit.

Any safety assessment visits during the washout period will be called V1a, V1b, etc. During these visits, the SBQ-ASC and any changes in medications since the previous visit will be obtained in addition to other assessments at the study clinician's discretion.

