### ***Visit 3 (V3) – Safety Dose / Day -7***

The intervention will occur the day after Baseline (V2). The participant may have this session  $\leq 7$  days following the Baseline visit (V2). If the participant is out of the  $\leq 7$  day

window, all baseline assessments are to be repeated. On the day of the intervention the following procedures will take place:

- Study intervention administration (Section 5.0): 1 oral dose of 10 mg of psilocybin administered in conjunction with supportive therapy (PAT).
- Vital signs (blood pressure and pulse) will be taken every 1.5 hours during this session.
- At least one therapist will be present in the room at all times during PAT and be available to respond to participants' physical and emotional needs.
- Participants will be instructed to lie on a bed in a non-clinical environment, and therapists will encourage participants to focus their attention inward and stay with any experience that arises. To enhance inward reflection, a pre-selected music playlist will be played. Administration of questionnaires or other instruments to be completed at the end of the dosing session when the acute effects of psilocybin have resolved:
  - Study team or therapist administered:
    - 11D-ASC to assess the acute drug effects
    - UKU Side Effect Scale
- The participant will be discharged 6-8 hours post-dosing when, in the opinion of the study PI (or delegate), the acute effects of psilocybin are resolved. The participant must be accompanied home by a caregiver who will remain with them for up to 24 hours after the dose was administered.
- Rescue medications are permitted during this visit as outlined in Section 5.6.

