## 6.2 Schedule of Events

### 6.2.1 Main Clinical Trial

| Procedures   | Screening Visit (V1) | Tapering Period (2-4 weeks) | Baseline Visit 2 (V2, Day -15 to Day -8) | Safety Dose (V3, Day -7) | Treatment Dose (V4, Day 0) | Study Visit 5 (V5, Day 1) | Study Visit 6 (V6, Week 1) | Study Visit 7 (V7, Week 2) | Study Visit 8 (V8, Week 4) | Study Visit 9 (V9, Week 12) |
|---|-----------------------------|--|---|---------------------------------|-----------------------------------|----------------------------------|-----------------------------------|-----------------------------------|-----------------------------------|------------------------------------|
| Location of Visit   | Clinic                      | Remote or Clinic                               | Clinic  | Clinic                          | Clinic                            | Clinic                           | Remote or Clinic                  | Remote or Clinic                  | Remote or Clinic                  | Remote or Clinic                   |
| Allowable Window  |                             | Weekly   |   | Within 7 days following V2      | Within 7-10 days following V3     | None                             | ±3 days                           | ±3 days                           | ±3 days                           | ±3 days                            |
| Informed consent  | X                           |  |   |                                 |                                   |                                  |                                   |                                   |                                   |                                    |
| Demographics  | X                           |  |   |                                 |                                   |                                  |                                   |                                   |                                   |                                    |
| Medical history   | X                           |  | X   |                                 |                                   |                                  |                                   |                                   |                                   |                                    |

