| Prior/Concomitant medication review                             | X                           | X  | X   | X                               | X                                 | X                                | X                                 | X                                 | X                                 | X                                  |
| Inclusion/Exclusion Criteria Review                             | X                           | X  | X   |                                 |                                   |                                  |                                   |                                   |                                   |                                    |
| Vital signs   | X                           |  | X   | X                               | X                                 |                                  |                                   |                                   |                                   |                                    |
| Height  | X                           |  |   |                                 |                                   |                                  |                                   |                                   |                                   |                                    |
| Weight  | X                           |  |   |                                 |                                   |                                  |                                   |                                   |                                   |                                    |
| Clinical laboratory tests                           | X                           |  |   |                                 |                                   |                                  |                                   |                                   |                                   |                                    |
| EKG/ECG   | X                           |  |   |                                 |                                   |                                  |                                   |                                   |                                   |                                    |

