| Urinalysis  | X                           |  |   |                                 |                                   |                                  |                                   |                                   |                                   |                                    |
| Urine drug screening  | X                           |  | X   |                                 |                                   |                                  |                                   |                                   |                                   |                                    |
| Urine Pregnancy test                                | X                           |  | X   |                                 |                                   |                                  |                                   |                                   |                                   |                                    |
| Documentation of birth control                                  | X                           |  |   |                                 |                                   |                                  |                                   |                                   |                                   |                                    |
| Preparatory/ Integrative therapy & psychoeducation  |                             |  | X   | X                               | X                                 | X                                | X                                 |                                   |                                   |                                    |

|   |   |   |   |   |   |   |   |   |   |   |
|---|---|---|---|---|---|---|---|---|---|---|
| Safety dose (10mg of psilocybin)  |   |   |   | X |   |   |   |   |   |   |
| Treatment dose (25mg of psilocybin)                                       |   |   |   |   | X |   |   |   |   |   |
| Adverse event and serious adverse event review plus UKU Side Effect Scale | X | X | X | X | X | X | X | X | X | X |
| CRF Completion  | X | X | X | X | X | X | X | X | X | X |
| 11D-ASC   |   |   |   | X | X |   |   |   |   |   |
| AAQ-II  |   |   | X |   |   |   | X |   | X | X |
| ABSI  |   |   | X |   |   | X | X | X | X | X |
| ADOS-2  | X |   |   |   |   |   |   |   |   |   |
| AQ-12   | X |   |   |   |   |   |   |   |   |   |
| ASA-A   |   |   | X |   |   |   | X |   | X | X |

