| ATHF  | X |   |   |   |   |   |   |   |   |   |
| BDI-II  |   |   | X |   |   | X | X | X | X | X |
| CAT-Q   | X |   |   |   |   |   |   |   |   |   |
| CD-RISC 10  |   |   | X |   |   |   | X |   | X | X |
| CFI   |   |   | X |   |   |   | X |   | X | X |
| CGI   |   |   | X |   |   |   | X |   | X | X |
| GAFS-8  |   |   | X |   |   |   | X |   | X | X |
| GRID-HAMD-17  | X |   | X |   |   |   | X |   | X | X |
| INQ-15  |   |   | X |   |   |   | X |   | X | X |
| ISQ-8   |   |   | X |   |   |   | X |   | X | X |
| RBQ-2A  | X |   |   |   |   |   |   |   |   |   |
| RRS-10  |   |   | X |   |   |   | X |   | X | X |
| RSPM  | X |   |   |   |   |   |   |   |   |   |
| SBQ-ASC   | X | X | X |   |   | X | X | X | X | X |
| SCID-5-CV   | X |   |   |   |   |   |   |   |   |   |
| SHAPS   |   |   | X |   |   |   | X |   | X | X |
| WHOQOL-4  |   |   | X |   |   |   |   |   | X | X |

|                            |  |  |   |  |  |   |  |  |  |   |
|----------------------------|--|--|---|--|--|---|--|--|--|---|
| Acceptability              |  |  |   |  |  |   |  |  |  | X |
| Avoid/Escape Go/No-Go task |  |  | X |  |  | X |  |  |  |   |
| Brain MRI      |  |  | X |  |  | X |  |  |  |   |

1. Additional visits may be needed during the washout period to ensure adequate time for discontinuation of medication. Visits will occur on a weekly basis during this period (V1a, V1b, etc.). Review of medications and assessments for suicidality will occur in addition to other assessments at the discretion of the study investigator.
2. Baseline assessments can occur on separate days (within 7 days from safety dose) to reduce the burden on participants. These visits will be V2a, V2b etc.
3. See Section 6.0: Research Procedures for complete list of required laboratory tests to be performed.
4. For women/females and people of child-bearing age only.
5. Additional therapy visits may be scheduled at the discretion of the study therapists and/or the study investigator and therapy can occur in-person or via WebEx.
6. To be administered immediately after the acute effects of psilocybin have subsided.
7. Required for the main clinical trial design, around 45 mins

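### The 25 mg dose is given on a suicidality rating 8 to 17 days old: neither suicidality nor eligibility is rechecked after V2, and no V4 safety review is timed before the capsule

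*Protocol*

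**What the plan says.** **V4 procedures.** Section 6.1.2.1 lists the 25 mg dose with supportive therapy, vital signs every 1.5 hours during the session, and the 11D-ASC and UKU as "instruments to be completed at the end of the dosing session when the acute effects of psilocybin have resolved". The V3 list has the same structure. Neither includes the SBQ-ASC.

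**Suicidality.** Exclusion criterion 11 in section 4.4.2 reads "Have active suicidal ideation with intent and plan as determined by SBQ-ASC", and section 8.5 relies on the same questionnaire for managing suicide risk. For washout, section 6.1.2.1 states: "Participants will be assessed for suicidality with the SBQ-ASC at each contact/visit". The row in schedule 6.2.1, in the order V1, tapering, V2, V3, V4, V5 to V9, is "SBQ-ASC | X | X | X | | | X | X | X | X | X". Both dosing visits are blank.

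**Eligibility.** The row "Inclusion/Exclusion Criteria Review" is ticked at V1, tapering and V2 only. Section 4.1 likewise requires the criteria to be met at V1 and V2. Section 4.7.1 lets the investigator withdraw a participant who newly meets an exclusion criterion.

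**Other reviews.** The row "Adverse event and serious adverse event review plus UKU Side Effect Scale" is ticked at every visit. Medication review is too, and vital signs are ticked at V3 and V4. None of these is placed before or after the capsule in the schedule.

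**Timing.** V3 falls within 7 days of V2. If that limit is missed, the text requires a repeat: "window, all baseline assessments are to be repeated". V4 is allowed "Within 7-10 days following V3".

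**The concern.** The 10 mg session is called the safety dose, yet no scheduled step uses what happens after it to decide whether 25 mg should follow. V3 does end with a UKU, a psychiatrist's evaluation before discharge (section 3.1) and a call to confirm arrival home (section 5.4). After that the main trial schedules no contact until V4; extra therapy visits are at the discretion of the therapists or the investigator.

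The withdrawal power in 4.7.1 and the urgent psychiatric assessment in 8.5 both require someone to notice a change first. Between the doses no suicidality rating is scheduled that would do so, although participants are still off antidepressants under section 5.6 and were rated weekly while tapering. Section 8.7 also cites 4.7.1 and 8.5 as part of the reason for having no independent monitoring board, which puts more weight on detection in the individual participant.

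Tolerability has the same gap. An effect of 10 mg that appears after V3 discharge gets its first scheduled UKU rating, for anyone outside the MRI sub-study, after 25 mg has been taken.

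**Working it through.** The plan states no figure for this interval, so it is built from the visit windows.

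**Inputs**
- V2 to V3: 1 day as planned, at most 7 days (6.1.2.1, Visit 3; schedule 6.2.1).
- V3 to V4: 7 to 10 days (schedule 6.2.1); 1 week in the Visit 4 text.
- V4 to V5: 1 day, no window (schedule 6.2.1).
- V2 day labels: Day -15 to Day -8, with V4 at Day 0.
- Sub-study uptake: 30 to 50% expected (section 2.4), of 20 participants.

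**Age of the SBQ-ASC at the 25 mg capsule** = (V2 to V3) + (V3 to V4)

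| Reading | Minimum | Maximum |
|---|---|---|
| Schedule windows | 1 + 7 = 8 days | 7 + 10 = 17 days |
| Visit 4 text, fixed week | 1 + 7 = 8 days | 7 + 7 = 14 days |
| Day labels | 0 − (−8) = 8 days | 0 − (−15) = 15 days |

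The minimum is 8 days on all three readings, and the rating always predates the 10 mg dose. The minimum is also the protocol's preferred case: V2 the day before V3, then V4 one week later.

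**Interval between SBQ-ASC ratings, V2 to V5:** 8 + 1 = 9 days to 17 + 1 = 18 days, against weekly during washout.

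**Comparison with the first dose.** At 10 mg, baseline assessments older than 7 days, the SBQ-ASC among them, must be repeated. At 25 mg they are at least 8 days old for every participant, and no repeat is required.

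**Last UKU before 25 mg.** Main trial: end of V3, so 7 to 10 days earlier. Sub-study: a visit one day after V3 (6.1.2.2 and schedule 6.2.2), so 7 − 1 = 6 to 10 − 1 = 9 days earlier. That visit has AE/UKU review and BDI-II but no SBQ-ASC. Section 3.1 instead lists this scan at V3; if that were followed, sub-study participants would have no contact between the doses either.

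**Participants with no scheduled visit between the doses.** Uptake of 50% gives 20 − 0.50 × 20 = 10; uptake of 30% gives 20 − 0.30 × 20 = 14. So 10 to 14 of 20.

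**After the fix.** With the SBQ-ASC done on the day of V4 before the capsule, its age is 0 days.

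**The case against.** The protocol is not silent on safety between the doses. AEs are sought by specific questioning at each contact (8.2), and at each visit staff ask about events since the previous one (8.5). Worsening of a pre-existing condition counts as an AE (8.1), and psychological distress is evaluated in all three study periods (3.2). A licensed physician gives the capsule (5.4), and a study psychiatrist is available throughout (3.1). The V4 list omits the AE and medication reviews that the schedule ticks, so it is not exhaustive and cannot show that they come after dosing. The 7-day repeat rule covers the whole baseline battery, MRI included, and may exist to keep pre-post baselines current. Some SBQ-ASC items look back over a lifetime or 12 months (6.1.1), so the questionnaire's age is an imperfect measure of missed acute change.

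Much of this is fair. Only the UKU is expressly placed at the end of V4; for the other reviews the point is that their timing is not fixed, not that they are known to come late. The 7-day rule is a comparison within the protocol, and exceeding it at V4 breaches no stated rule. The look-back of the SBQ-ASC is a reason to add a direct clinical question. The 17-day maximum depends on the schedule's 7 to 10 day window.

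None of it supplies what is missing. No safeguard cited includes a suicidality rating, an exclusion review or a recorded decision that must come before the 25 mg capsule. The V3 discharge evaluation is 7 to 10 days old by then. The instruction to use the SBQ-ASC at every contact belongs to the washout section, and both the V4 procedure list and the schedule leave it out.

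**Conclusion.** The concern holds. Followed as written, the protocol gives 2.5 times the first dose (25/10) with no scheduled suicidality rating or eligibility review since before that first dose. The rating is 8 to 17 days old under the schedule windows, 8 to 14 or 8 to 15 days on the narrower readings, and never less than 8. At the expected sub-study uptake, 10 to 14 of 20 participants also have no scheduled visit between the doses.

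This assumes that V2 is at least one day before V3, as the Visit 3 text plans, and that staff do only what the protocol schedules. Clinicians may well ask about suicidality before dosing, but the protocol neither requires nor documents it. Because this concerns participant safety and the correction is small, it should be fixed.

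**What to change.** Amend section 6.1.2.1 (Visit 4) and schedule 6.2.1 so that the following are completed before the 25 mg capsule:

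1. SBQ-ASC, with a V4 tick, plus a direct question from the study physician on current ideation, intent and plan.
2. AE/UKU review covering the time since V3, keeping the end-of-session UKU.
3. One vital-sign reading.
4. A review of the exclusion criteria, with a V4 tick and the study physician's recorded decision to proceed or to withdraw the participant under 4.7.1. The decision should expressly cover anyone given a rescue antipsychotic at V3.

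The clinical thresholds are for the investigators to set.

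**Cost.** A protocol and CRF amendment, and roughly 15 to 20 minutes before dosing. That time is an estimate and could be longer, since the adapted UKU has 35 items. Participant, physician and therapists are already on site, and no new instrument or staff is needed. Some participants may be deferred beyond the 7 to 10 day window or withdrawn, and withdrawals would count against the retention target of more than 90% in Hypothesis 1a.
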